Subjects will be screened up to seven days in advance of the vaccine administration and will demonstrate a satisfactory baseline medical assessment by medical history, general physical examination, urinalysis, haematological and blood biochemistry analyses, and serum screening for HIV, Hepatitis B and Hepatitis C markers. On Day 0, vaccine administration will occur. Phone contacts will be made one day and eight days after the vaccine administration, specifically for review of the subject's safety and concomitant medication data. Visits to the Investigator site will occur 3 days after the vaccine administration (Day 3) for key safety assessments and 28 days after the vaccine administration (Day 28) for key safety and immunogenicity assessments. Subjects will have monthly telephone calls after Day 28 up to the end of the study. Subjects will return to the Investigator site on Day 182 for immunogenicity and safety assessments (6-month follow-up) and on Day 365 for final immunogenicity and safety assessments (12-month follow-up).

Subjects enrolled and vaccinated in the QVLP (15 μ g/strain and 45 μ g/strain) adjuvanted with AS03 adjuvant (full dose or half dose) and the QVLP (30 μ g/strain) adjuvanted with AS03 adjuvant (half dose) treatment groups will complete study procedures as outlined above and will be followed for safety and immunogenicity assessments up to Day 365.

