The Investigator will be instructed to closely monitor each subject who experiences an AE (whether ascribed to the investigational product or not) until the outcome of the AE has been determined.

If any of the solicited local or systemic AEs persist beyond Day 7, these will also be recorded as unsolicited AEs. In this case, the AE start will be set as eight days post-vaccination. The subject will be requested to note when the AE resolves and to report this information to the Investigator or clinic staff at the next visit at the clinical site or contact.

The clinical importance of AEs will be determined based upon the Investigator's judgment. The Investigator must ensure that any sample obtained to follow-up on an AE is properly labeled and stored. The Investigator and others responsible for care of the subjects should institute any supplementary investigations of significant AEs based on the clinical assessment of the likely causative factor. This may include seeking the opinion of a specialist in the field of the AE.

All unsolicited AEs occurring within 28 days after vaccination must be reported in the "Adverse Event" screen in the subject's eCRF, irrespective of intensity or whether or not they are considered to be vaccination-related. Thereafter, from Day 29 through to Day 365, SAEs, AEs leading to withdrawal, AESIs, MAAEs, and NOCDs (see Section 13.1.4 for definition) will be monitored and reported in the eCRF. Additional details on eCRF entries can be found in the eCRF completion guidelines.

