13.1.4 New Onset of Chronic Disease

In the context of this study, all NOCDs that may plausibly have an allergic, autoimmune or inflammatory component are to be reported. Plausibility should be interpreted broadly however; the only clear exceptions are degenerative conditions such as osteoarthritis, age-related physiologic changes (e.g. benign prostatic hypertrophy) and life-style diseases (e.g. alcohol-associated cirrhosis, bronchitis in a smoker, etc.). In this context, most cancers, cardiac conditions and kidney diseases should be reported.

NOCDs will be collected from vaccination on Day 0 to Day 365 and reported as an AE or SAE, as applicable.

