13.1.6 Initial SAE Reporting by the Investigator

Details on safety reporting are defined in study-specific documentation, including SAE processing, country-specific reporting requirements, regulatory unblinding, roles and responsibilities of different stake holders, and contact details of personnel responsible for safety reporting. A brief summary of salient information is presented below.

All post-vaccination SAEs and AESIs will be reported from the time of receiving the study vaccine on Day 0 through to the end of the study (final scheduled visit). The Investigator (or designee) must report, by e-mail, all SAEs and AESIs, whether considered related to the study vaccine or not to Medicago (or its designee) within 24 hours of the Investigator learning of the event. The Investigator must also complete the electronic SAE/AESI form in the electronic data capture (EDC) database within 24 hours of awareness of the event following the Electronic Case Report Form Completion Guidelines (eCCG). An automatic email notification will be sent to the Medicago Clinical Safety mailbox after the Investigator submits the electronic SAE/AESI form. If the EDC database is not available, the Investigator must complete, sign, and date the paper SAE/AESI report form, and send, via e-mail, a copy to the Medicago safety e-mail address (listed below) and the appropriate regional e-mail address, as required, within 24 hours of awareness of event. If the SAE/AESI paper reporting process is followed, the Investigator will need to enter the SAE/AESI information in the EDC system once available.

Medicago Safety e-mail address: [contact]

Sponsor Safety Contact:

Serious AEs will be reported to the local (or contract) IRB by the Investigator according to the IRB's policy and procedures.

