Subjects will be screened up to seven days in advance of the vaccine administration and will demonstrate a satisfactory baseline medical assessment by medical history, general physical examination, urinalysis, haematological and blood biochemistry analyses, and serum screening for HIV, Hepatitis B and Hepatitis C markers. On Day 0, vaccine administration will occur. Phone contacts will be made one day and eight days after the vaccine administration, specifically for review of the subject's safety and concomitant medication data. Visits to the Investigator site will occur 3 days after the vaccine administration (Day 3) for key safety assessments and 28 days after the vaccine administration (Day 28) for key safety and immunogenicity assessments. Subjects will have monthly telephone calls after Day 28 up to the end of the study. Subjects will return to the Investigator site on Day 182 for immunogenicity and safety assessments (6-month follow-up) and on Day 365 for final immunogenicity and safety assessments (12-month follow-up). The schedule of events to be performed from screening visit to all post-vaccination visits/contacts is presented in Appendix 13.1.

Subjects enrolled and vaccinated in the QVLP (15  $\mu$ g/strain and 45  $\mu$ g/strain) adjuvanted with AS03 adjuvant (full dose or half dose) and the QVLP (30  $\mu$ g/strain) adjuvanted with AS03 adjuvant (half dose) treatment groups will complete study procedures as outlined above and will be followed for safety and immunogenicity assessments up to Day 365.

Medicago USA Page 12 of 55

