When count data are presented, the percentage will be suppressed when the count is zero in order to draw attention to the non-zero counts. A row denoted "Missing" will be included in count tabulations where specified on the shells to account for dropouts and missing values. The denominator for all percentages will be the number of subjects in that clinical diagnosis category within the analysis set of interest, unless otherwise specified.

Baseline value is defined as the last non-missing data on or before the IM injection of the study vaccine, unless otherwise specified.

Study Day is the number of days since the administration of the study vaccine, which is counted as Study Day 0. If the assessment date is after the date of the vaccination, the study day is calculated as date of assessment - date of the vaccination + 1. If the assessment date is prior to the date of the vaccination, the study day is calculated as date of assessment - date of the vaccination.

Medicago USA Page 17 of 55

Onset day is calculated as date of event – date of the vaccination +1.

During the programming period, the table/listing/figure shell format and footnote might be edited. And this kind of change is not be considered as analysis changes or impact the analysis results.

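### The SAP's day-count formulas run one day ahead of the protocol's numbering, so no reading of the safety windows reproduces the Day 28 and Day 182 splits in the primary safety endpoints

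*SAP*

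**What the plan says.** SAP Section 4 defines the day count in words: "Study Day is the number of days since the administration of the study vaccine, which is counted as Study Day 0". For dates after vaccination it then gives a formula that does not match: "the study day is calculated as date of assessment - date of the vaccination + 1". Dates before vaccination use the simple difference. A separate line covers events: "Onset day is calculated as date of event" minus the vaccination date, plus 1.

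The rest of the trial counts elapsed days. Protocol Section 4.1 places a visit "3 days after the vaccine administration (Day 3) for key safety assessments", and SAP Section 3.1 places another "28 days after the vaccine administration (Day 28) for key safety and immunogenicity assessments". Protocol Section 13.1.2 dates a solicited AE that outlasts Day 7 the same way: "the AE start will be set as eight days post-vaccination".

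SAP Sections 9.3.3 to 9.3.8 tabulate SAEs, AESIs, MAAEs, NOCDs, AEs leading to discontinuation and AEs leading to death in three windows: Day 1 to 28, Day 29 to 182, and Day 183 to the end of the study. Events are placed by AE analysis start date. The day variable is not named.

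The primary safety endpoints (Protocol Section 10.2.2.1, SAP Section 3.2.1) use the same upper limits, but their first period has no Day 1 lower limit. Collection starts on the vaccination day: "NOCDs will be collected from vaccination on Day 0 to Day 365", and "All post-vaccination SAEs and AESIs will be reported from the time of receiving the study vaccine on Day 0".

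**The concern.** Section 4 of the SAP contradicts itself. With vaccination as Day 0 and 1 added to every later date, the day after vaccination is Study Day 2 and Study Day 1 does not exist. The vaccination day is at once Study Day 0 and Onset day 1. After vaccination, both formulas run one day ahead of the visit and endpoint numbering.

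The windowed tables report primary safety endpoints. If the day variable is off by one, events on the boundary days are reported in the wrong period. If the first window starts at Day 1 on an elapsed count, vaccination-day events drop out of these tables. Two programmers following the text could also produce different counts from the same data.

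**Working it through.** The plan gives no figure to reproduce, so the check is date arithmetic.

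**Inputs.** Let d be the event start date minus the vaccination date.
- Onset day (SAP Section 4): d + 1.
- Study Day (SAP Section 4): 0 at d = 0, and d + 1 for d > 0.
- Plain elapsed count (the SAP's worded definition and the protocol's usage): d.
- SAP windows (Sections 9.3.3 to 9.3.8): 1–28, 29–182, 183 onward.
- Endpoint windows (Protocol Section 10.2.2.1, with collection from Day 0): 0–28, 29–182, 183 onward.
- Range: d = 0 to 379, that is, the Day 365 visit plus its 14-day allowance. The last window is taken as open-ended because it runs to the end of the study.

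**Boundary days under each count**

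| d | Endpoint window | Onset day | Study Day | Plain count |
|---|---|---|---|---|
| 0 | first | 1, first | 0, **none** | 0, **none** |
| 27 | first | 28, first | 28, first | 27, first |
| 28 | first | 29, **second** | 29, **second** | 28, first |
| 181 | second | 182, second | 182, second | 181, second |
| 182 | second | 183, **third** | 183, **third** | 182, second |
| 183 | third | 184, third | 184, third | 183, third |

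**Calendar days in each window, d = 0 to 379**

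| Count | First | Second | Third | Unassigned | Differs from endpoints at |
|---|---|---|---|---|---|
| Endpoints | 29 | 154 | 197 | 0 | – |
| Onset day | 28 (d = 0–27) | 154 | 198 | 0 | d = 28, 182 |
| Plain count | 28 (d = 1–28) | 154 | 197 | 1 | d = 0 |
| Study Day | 27 (d = 1–27) | 154 | 198 | 1 | d = 0, 28, 182 |

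If the last window is instead closed literally at Day 365, Onset day and Study Day also put d = 365 outside every window, since each numbers it 366.

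The protocol's imposed start at d = 8 becomes Onset day 9. This crosses no boundary, but it shows that the two systems differ.

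**Size.** The documents give no SAE or MAAE rate for this vaccine with AS03, so the following is an assumption. Suppose 5%, 20% or 50% of 40 subjects per arm have one event each, with starts spread evenly over the 366 days d = 0 to 365. Expected events starting on d = 28 or 182 are n × 2/366:
- n = 2: 2 × 2/366 = 0.011 per arm; × 3 arms = 0.033.
- n = 8: 8 × 2/366 = 0.044 per arm; × 3 arms = 0.131.
- n = 20: 20 × 2/366 = 0.109 per arm; × 3 arms = 0.328.

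This covers days 28 and 182 only. An even spread is not credible for the vaccination day, because SAP Section 4.3 moves many partial AE start dates to that day and immediate allergic reactions would start then. No figure is offered for d = 0.

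**The case against.** The strongest reply is that Section 4 ties Study Day to assessments and Onset day to events. The windows concern events and begin at Day 1, which is the vaccination day on the Onset-day count. Formula and label then fit together and nothing is left unassigned. On that reading the only defect is a one-day shift at two boundaries. This is the likeliest reading, and the loss of vaccination-day events is the secondary case. However, the SAP never says that Onset day drives the windows, and on that reading the first window still ends at 27 elapsed days, short of the endpoint.

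It is also true that no event disappears from the safety output as a whole. SAP Section 9.1 summarises the same categories without these windows, Section 9.3 tabulates them by sex, race and prior vaccination, and all events are listed. Scheduled laboratory summaries use nominal visit dates, so they are unaffected. Only the tables split by period change.

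Finally, the three-arm total is incomplete. SAP Section 4 keeps the five stopped groups in the analyses, and their sizes are not given. That limits the total but not the per-arm figures.

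**Conclusion.** The concern holds and is minor. Onset day misplaces days 28 and 182, the plain count omits day 0, and the Study Day formula does both. No reading of SAP Section 4 with Sections 9.3.3 to 9.3.8 reproduces the periods in the primary safety endpoints.

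Under the stated assumptions, about 0.01 to 0.11 events per arm would start on day 28 or 182, or 0.03 to 0.33 over the three current arms. These figures rest on the assumed event rates and an even spread of starts. The list of misplaced days rests on an open-ended last window. SAP Section 9 makes safety descriptive with no tests, so no conclusion is likely to change. The intended count can be recovered from the rest of the documents. The formulas and the Day 1 label are what is wrong.

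**What to change.** In SAP Section 4, define Study Day and Onset day both as the date minus the vaccination date, with vaccination as Day 0. State in Section 9.3 that this variable, computed from the AE analysis start date, drives the windows. In Sections 9.3.3 to 9.3.8, relabel the first window Day 0 to Day 28. Keep the last as Day 183 to end of study, noting that Day 365 is nominal because that visit has a window of ±14 days.

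Keeping Onset day and moving the boundaries to 1–29, 30–183 and 184 onward would give the same periods, but the labels would no longer match the protocol.

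The cost is SAP wording, one derivation in the analysis datasets, one label in six subsections, and a check of any Day 28 or Day 182 interim tables already produced under SAP Section 10. No new data are needed.

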# 4.1. Sample Size

No statistical sample size calculations were performed. The determined sample size up to approximately 120 subjects with 40 subjects in each treatment group will make it possible to perform the initial evaluation of vaccine immunogenicity and detect sizable differences in rates of adverse events since objective of this study is to quantify the type, percentage, intensity, duration, and relationship of common post-vaccination safety events to determine if they differ clinically among the treatment groups.

### 4.2. Randomization, Stratification, and Blinding

#### 4.2.1. Randomization and Stratification

The randomization numbers will be allocated to subjects within the appropriate treatment group by the randomization system once all screening procedures, including Day 0 prerandomization procedures, have been completed and the study eligibility is confirmed by the Investigator. Randomization will be stratified by age group (65 to 74 years of age and 75 years of age and older). In addition, after the implementation of the new randomization strategy per protocol version 3.0, prior influenza vaccination status (defined as having received a standard influenza vaccine during the 12 months prior to study vaccination) was also added as a stratification factor (i.e., it was not in place for the randomization of any subjects enrolled prior to protocol version 3.0).

Considering the study design with two scheduled IDMCs, as per protocol version 1.0, the randomization schedule was to include subjects in treatment groups 1-6 and begin the enrolment in treatment groups 7 and 8 once 1st IDMC permits. However, as described previously, two treatment groups (QVLP adjuvanted with AS03 (half dose) 15 ug/strain and QVLP adjuvanted with AS03 (half dose) 45 ug/strain) in protocol version 3.0 and three treatment groups (QVLP adjuvanted with AS03 15 µg/strain, QVLP adjuvanted with AS03 (half dose) 30 µg/strain and QVLP adjuvanted with AS03 45 µg/strain) in protocol version 4.0 were stopped.

The randomization of the two stopped treatment groups in protocol version 3.0 was generated according to the randomization schema (with age group only as stratification factor) planned in the protocol version 1.0 (refer to Appendix 13.2). Some patients enrolled in the 3 treatments groups stopped in protocol version 4.0 were randomized according to the new randomization schema (with age and influenza history vaccine as stratification factor). Patients enrolled after the implementation of protocol version 4.0 will be randomized into the three remaining treatment groups. The randomization schedule will be generated by computer.

Medicago USA Page 18 of 55

Once a randomization number has been assigned, it will not be re-used for any reason. No subjects will be randomized into the study more than once. If a randomization number is allocated incorrectly, no attempt will be made to remedy the error once the study vaccine has been dispensed: the subject will continue on the study with the assigned randomization number and associated treatment and the admission of subsequent eligible subjects will continue using the next unallocated number in the sequence.

If a subject is randomized in error (i.e., does not meet eligibility criteria) and has not been vaccinated, then another eligible subject can be randomized to replace this subject. Subjects who withdraw or are withdrawn from the study after vaccination will not be replaced.

Medicago USA Page 19 of 55

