4.2 Rationale of Study Design

4.2.1 Randomization

Randomization will be used to minimize bias in the assignment of subjects to treatment groups, to increase the likelihood that known and unknown subject attributes (e.g. demographic and baseline characteristics) are evenly balanced across treatment groups, and to enhance the validity of statistical comparisons across treatment groups.

Subjects will be randomized according to prior influenza vaccination status defined as enrolled subjects who have received a standard influenza vaccine during the 12 months prior to study vaccination.

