6 TREATMENT ALLOCATION AND BLINDING

6.1 Randomization

Potential study subjects will be screened and assigned a six-digit subject number. Once all screening procedures, including Day 0 pre-randomization procedures, have been completed and the study eligibility is confirmed by the Investigator, the randomization numbers will be allocated to subjects within the appropriate treatment group by the randomization system. If a subject is randomized in error (i.e. does not meet eligibility criteria) and has not been vaccinated, then another eligible subject can be randomized to replace this subject.

Once a randomization number has been assigned, it will not be re-used for any reason. No subjects will be randomized into the study more than once. If a randomization number is allocated incorrectly, no attempt will be made to remedy the error once the study vaccine has been dispensed: the subject will continue on the study with the assigned randomization number and associated treatment. The study staff will notify the Sponsor Contact as soon as the error is discovered without disclosing the study vaccine administered. Admission of subsequent eligible subjects will continue using the next unallocated number in the sequence.

Randomization will be stratified by prior influenza vaccination status (defined as enrolled subjects who have received a standard influenza vaccine during the 12 months prior to study vaccination). Subjects will then be enrolled into one of three treatment groups, based on a computer-generated randomization schedule prepared by or under the supervision of Medicago before the study. The randomization number and treatment will be recorded for each subject in the investigational product accountability log.

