# 3. Investigational Plan

# 3.1. Overall Study Design and Plan

This randomized, partially-blinded, active comparator-controlled multi-center, Phase 1/2 study will be conducted at multiple sites to evaluate the safety, tolerability, and immunogenicity of an adjuvanted seasonal recombinant quadrivalent VLP influenza vaccine in adults 65 years of age and older. Overall approximately 120 healthy male and female subjects 65 years of age and older will be enrolled evenly into one of three parallel treatment groups and subjects will be stratified by age into two groups (65 to 74 years of age and 75 years of age and older) and by prior influenza vaccination status (defined as having received a standard influenza vaccine during the 12 months prior to study vaccination). Before protocol version 4.0 became effective:

- In protocol version 2.0, a different randomization was in place with 2 additional treatment groups (QVLP adjuvanted with AS03 (half dose) 15 μg/strain and QVLP adjuvanted with AS03 (half dose) 45 μg/strain) and without prior influenza vaccine status as randomization stratification factor. The enrollment of these two treatment groups was stopped per protocol version 3.0. The number of subjects randomized into these two treatment groups will be documented in the CSR. The six treatment groups included three dose levels of QVLP (15 μg/strain, 30 μg/strain, and 45 μg/strain) with the full dose or QVLP (30 μg/strain) with the half dose of adjuvant AS03, unadjuvanted full dose of QVLP (30 μg/strain), and the active comparator Fluzone HD Quad.
- In protocol version 3.0, there was 3 additional treatments groups (QVLP adjuvanted with AS03 15 μg/strain, QVLP adjuvanted with AS03 (half dose) 30 μg/strain and QVLP adjuvanted with AS03 45 μg/strain). The enrollment of these 3 treatment groups was stopped per protocol version 4.0. The number of subjects randomized into these three treatment groups will be documented in the CSR. Moreover, the planned number of subjects has been decreased 50 to 40 by treatment group.

The three remaining treatment groups include QVLP adjuvanted with AS03 (30 µg/strain), unadjuvanted QVLP (30 µg/strain), and the active comparator Fluzone HD Quad.

**Table 1:** Study Treatment Groups

Treatment Group	Treatments	Dose Level	Planned No. of Subjects
1	QVLP adjuvanted with AS03	30 μg/strain	40
2	QVLP unadjuvanted	30 μg/strain	40
3	Fluzone HD Quad	60 μg/strain	40

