# To calculate adjusted GMFR and do the ANCOVA:

PROC MIXED data=tab(where=(avisitn = Day <0, 28, 182, 365>)); \*\* to be repeated for each relevant timepoints

BY STRAIN;

CLASS TRT:

MODEL var = TRT BASE; \*\* where var=LOG10(Analysis value/Baseline value) and BASE is LOG10(Baseline value)

LSMEANS TRT / DIFF=ALL CL ALPHA=0.05 ADJUST=tukey;

RUN;

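### Protocol and SAP name different randomisation strata, and no between-arm immunogenicity comparison adjusts for any of them

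*SAP*

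**What the plan says.** **Randomisation factors.** Protocol 6.1 says "Randomization will be stratified by prior influenza vaccination status", and protocol 4.2.1 says "Subjects will be randomized according to prior influenza vaccination status". Neither section mentions age. SAP 3.1, describing the current three-arm design of about 120 subjects, says "subjects will be stratified by age into two groups" and adds prior vaccination. SAP 4.2.1 also says "Randomization will be stratified by age group". It dates prior vaccination as a factor from protocol version 3.0 and notes that "it was not in place for the randomization of any subjects enrolled prior to protocol version 3.0". SAP 6.1 tabulates the four age-by-vaccination cells as a baseline characteristic.

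**Comparisons.** In SAP 13.3 the GMT model has treatment as its only term. The GMFR model is "MODEL var = TRT BASE", where the covariate is log10 baseline titer. SAP 8.1 compares seroconversion (SC) and seroprotection (SP) rates by Fisher's exact test without strata. Prior vaccination is used only to repeat analyses by status, and only if more than 25% of enrolled subjects had been vaccinated (SAP 8.2). Age group appears in no comparison.

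**The concern.** There are two linked problems.

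First, a reader of both documents cannot tell how subjects were allocated. The protocol gives one factor and the SAP gives two, and the scheme changed during the study in a way that the protocol's description does not show.

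Second, whichever document is right, the factors used to balance the arms are absent from the analysis. Stratifying makes the arms more alike on those factors than chance would. A model without them still counts between-stratum variation as error. The reported standard error then exceeds the true one for a factor that was balanced by design. For subjects randomised before version 3.0, prior vaccination was not balanced by design. There the unadjusted interval is valid, but it is less precise than an adjusted one if the factor is prognostic.

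At stake is the precision of the primary HI contrasts in a study with 40 subjects per arm.

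**Working it through.** **Text comparison**

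| Source | Age group | Prior vaccination |
|---|---|---|
| Protocol 4.2.1, 6.1 | not named | yes |
| SAP 3.1 (current design) | yes | yes |
| SAP 4.2.1, before protocol v3.0 | yes | no |
| SAP 4.2.1, from protocol v3.0 | yes | yes |
| GMT ANOVA (SAP 13.3) | no | no |
| GMFR ANCOVA (SAP 13.3) | no | no |
| Fisher's exact test, SC and SP (SAP 8.1, 13.3) | no | no |

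**Is there a figure to reproduce?** No. SAP 4.1 states that no sample size calculation was made, and neither document gives an SD, effect size or power. The only arithmetic is 3 × 40 = 120.

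**Size of the loss, GMT model.** Let R² be the share of within-arm log-titer variance that the two factors explain. This is an assumption; the range shown is 5-20%.

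- Adjusted over unadjusted CI width = √(1 − R²).
- Equivalent sample size per arm = 40/(1 − R²).
- True level of one nominal 5% unadjusted comparison, if both factors are balanced by design = 2[1 − Φ(1.96/√(1 − R²))].

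| R² | Width ratio | Narrower by | Equivalent n per arm | True level |
|---|---|---|---|---|
| 0.05 | 0.975 | 2.5% | 42.1 | 4.4% |
| 0.10 | 0.949 | 5.1% | 44.4 | 3.9% |
| 0.20 | 0.894 | 10.6% | 50.0 | 2.8% |

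The width ratio does not depend on the number of arms. It would be the same if the stopped groups, which SAP section 4 also brings into the analyses, were in the model.

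**Simulation, both models.** The assumptions below are not in the documents:

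- three arms of 40, with four equal strata balanced across arms;
- SD 0.5 on the log10 scale and a 2-fold GMT ratio;
- baseline to Day 28 residual correlation 0.5;
- each factor explains half of R²; prior vaccination shifts baseline and Day 28 titers, and age shifts Day 28 only;
- Tukey pairwise tests and 3,000 runs per scenario.

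| R² | GMT power, without / with strata | GMFR power, without / with strata | GMFR standard error, without / with strata |
|---|---|---|---|
| 0.05 | 0.61 / 0.64 | 0.77 / 0.78 | 0.0966 / 0.0945 |
| 0.10 | 0.63 / 0.68 | 0.78 / 0.81 | 0.0963 / 0.0922 |
| 0.20 | 0.64 / 0.74 | 0.80 / 0.86 | 0.0956 / 0.0868 |

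The GMFR standard-error ratios are 0.0945/0.0966 = 0.978, 0.0922/0.0963 = 0.957 and 0.0868/0.0956 = 0.908. GMFR intervals are therefore 2.2%, 4.3% and 9.2% narrower, a little less than for GMT in each row. If R² = 0 there is no loss in either model.

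**Cost in degrees of freedom.** The three-arm ANOVA goes from 120 − 3 = 117 residual degrees of freedom to 115, and the ANCOVA from 116 to 114.

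**The case against.** The strongest case on the other side has five parts.

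- **The SAP already gives the factors by protocol version.** This stands. The gap is that the protocol omits age. SAP section 11 lists changes to analyses, so its silence on randomisation factors is weak evidence of a fault. One might suppose that age was dropped in a later protocol version, but neither document says so, and SAP 3.1 applies both factors to the current design.
- **A baseline-adjusted comparison is already planned.** This stands. Modelling log fold rise on treatment and log baseline gives the same treatment contrasts as modelling log Day 28 titer on those terms. It would be wrong to infer that all the precision from stratifying is thrown away. GMT, SC and SP have no such adjustment.
- **The unadjusted analysis is valid.** This stands. A reader might infer that the treatment comparisons are biased, or that adjustment is the only protection for subjects randomised before version 3.0. Neither follows. Randomisation and the confidence intervals allow for chance imbalance, GMFR adjusts for baseline titer, and by-status repeats are planned above the 25% threshold.
- **The gain is assumed, and no decision rule rests on it.** This stands as a limit on size. The study is exploratory. Exclusion criterion 5 bars influenza vaccine within six months, so the vaccinated stratum is confined to those vaccinated roughly 6 to 12 months earlier and may be small. The improvement remains nearly free.
- **Changing the model now follows unblinded looks.** SAP version 5.0 is dated March 2022, after an interim analysis of HI data transferred on 12 February 2021, and selected sponsor staff can see data throughout. This bears on how the change is made and reported. It does not argue against two pre-vaccination factors that the SAP already names.

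**Conclusion.** The concern holds in a limited form. The mismatch in stratification factors and the absence of both factors from every between-arm comparison are certain from the text. The consequence is unnecessary width and conservatism if the factors are prognostic, with no bias in the treatment comparison. For factors explaining 5-20% of residual variance, intervals would be about 2.5-10.6% narrower, equivalent to about 42-50 subjects per arm instead of 40. The loss is greatest for GMT and smaller for GMFR. That range is an assumption. The documents supply nothing to fix it, and the true gain could be negligible. The change should be made because it costs so little, not because the planned results would be invalid.

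**What to change.** 1. Check the randomisation list, then bring protocol 4.2.1 and 6.1 into line with SAP 3.1 and 4.2.1, stating which factors applied under each protocol version.
2. In SAP 13.3, add both factors to the CLASS and MODEL statements: `MODEL var = TRT AGEGRP PRIORVAC` for GMT and `MODEL var = TRT BASE AGEGRP PRIORVAC` for GMFR.
3. Derive both from recorded data for every subject, including those randomised before version 3.0. Protocol 10.1.3 collects date of birth, age and influenza vaccinations over the previous 24 months, so nothing new is needed.
4. Add a stratified comparison for SC and SP, for example Cochran-Mantel-Haenszel. The by-arm rates and their Clopper-Pearson intervals can stay as planned.
5. Record the change in SAP section 11, with its date relative to the interim analyses, and report the current unadjusted models and Fisher tests alongside.

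The cost is two degrees of freedom, SAP and protocol wording, and a little extra programming.
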